7 SAFETY ASSESSMENTS AND REPORTING

7.1 **Definitions**

7.1.1 Adverse Event

An AE is any untoward medical occurrence in a patient or clinical investigation participant administered a pharmaceutical product and that does not necessarily have a causal relationship with this treatment. An AE can therefore be any unfavorable and unintended sign (including an abnormal laboratory finding), symptom, or disease temporally associated with the use of a medicinal (investigational) product, whether or not related to the medicinal (investigational) product.

Notes:

- A diagnosis should be captured as an AE term and signs and symptoms should be captured only in the absence of a unifying diagnosis. If a diagnosis is ultimately made, it should replace the previous report based on signs and symptoms.
- *In the event that there are multiple diagnoses, then all diagnoses should be captured.*
- The worsening of an existing sign, symptom or disease is also considered to be an AE.
- An abnormal laboratory finding deemed by the principal investigator (or designee) as not clinically significant (NCS) will not be captured as an AE, but an abnormal laboratory finding that worsens after dosing with the IP, from not clinically significant to clinically significant (CS), is considered an AE.
- Surgical procedures are not AEs. They are the action taken to treat a medical condition. Interventions that were planned prior to study entry for medical conditions that started prior to study entry but did not worsen during the clinical study are not reported as AEs.
- Medically attended adverse events: medically attended visits include hospital, emergency room, urgent care clinic, or other visits to or from medical personnel. Routine scheduled study visits will not be considered medically attended visits.

7.1.2 Solicited Adverse Event

A solicited AE is a protocol-specified AE about which the investigator (or designee) proactively asks the participants during a protocol-specified time period. A reactogenicity event may be considered as a solicited AE per discretion of the investigator (as described below in Section 7.1.2.1).

7.1.2.1 Reactogenicity

Reactogenicity (solicited systemic and local injection site reactions) will be assessed by the participants using e-diary cards. Information will be solicited on the following injection site reactions: pain, redness, and swelling. In addition, information will be solicited for AEs, on the following systemic reactions: temperature increases (oral) \geq 38.0°C (\geq 100.4°F), chills, fatigue, headache, myalgia, arthralgia, and nausea.

If injection site or systemic reactions continue beyond seven days postvaccination, these will be recorded in the EDC as unsolicited AEs. For any type of reactogenicity persisting two weeks or more, the investigator (or designee) will evaluate the reaction at the next scheduled visit and/or determine based on the nature and severity if a more immediate unscheduled follow-up visit is required to fully assess the reaction.

7.1.3 Unsolicited Adverse Event

An unsolicited AE is an AE that is spontaneously reported by the participant or discovered by the investigator.

7.1.4 Adverse Event of Special Interest

Arthralgia will be included as an AESI. The occurrence of new onset or worsening arthralgia that is medically attended will be monitored throughout the study for all participants. Medically attended visits include hospital, emergency room, urgent care clinic, or other visits to or from medical personnel. Routine scheduled study visits will not be considered medically attended visits.

7.1.5 Serious Adverse Event

An SAE is any untoward medical occurrence that: results in death, is life threatening, requires inpatient hospitalization or prolongation of existing hospitalization, results in persistent or significant disability/incapacity or substantial disruption of the ability to conduct normal life functions, or is a congenital anomaly or birth defect.

Important medical events which may not result in death, be life threatening, or require hospitalization may be considered an SAE when, based upon appropriate medical judgment, they may jeopardize the patient or participant and may require medical or surgical intervention to prevent one of the outcomes listed in this definition.

Notes:

- Death is an outcome and not an event. The condition leading to death is the event. If no other information regarding the cause of death is available, the event will be considered "Unspecified Adverse Event".
- Overnight stay at hospital/clinic that occurs during a study for social reasons (eg, transportation difficulties, respite care) is not considered to be a hospitalization event.

7.1.6 Suspected Unexpected Serious Adverse Reaction

Suspected Unexpected Serious Adverse Reaction (SUSAR) is the term used to refer to an AE that occurs in a clinical study participant, which is assessed by the sponsor and or study investigator as being unexpected, serious, and as having a reasonable possibility of a causal relationship (Section 7.1.8) with the IP.

7.1.7 Severity of Adverse Events

The investigator will grade all adverse events for severity. Adverse events listed in the grading scale in Appendix I will be graded according to the criteria in the table. Adverse events not listed in the grading scale will be graded as follows:

- Mild (Grade 1): No interference with activity
- Moderate (Grade 2): Some interference with activity
- Severe (Grade 3): Significant; prevents daily activity
- **Potentially Life-Threatening (Grade 4):** As determined by emergency room visit or hospitalization.

For the study grading scale see Appendix I.

7.1.8 Causality of Adverse Events

The investigator is responsible for the assessment of the causality of an AE and sponsor's MM will also assess SAE causality, independent of the investigator.

The following guidelines are provided for this assessment:

- Unrelated: No relationship between the IP and the reported event.
- **Possibly related:** The event follows a reasonable temporal sequence from the time of administration of IP and/or follows a known response pattern to the IP but could also have been produced by other factors.
- **Probably related:** A reasonable temporal sequence of the event with administration of IP exists and based on the known response to the IP, known or previously reported adverse reactions to the IP or similar products, or in the investigator's (or designee) clinical judgment the association of the event with the IP seems likely.

If the relationship between the AE and the IP is determined to be "possible" or "probable", the event will be considered to be "related" to the IP, otherwise it will be considered "not related" for reporting purposes.

7.2 Eliciting Adverse Events

Adverse events reported spontaneously by the participant in response to an open question from the principal investigator (or designee) or revealed by observation (eg, during physical exam) will be recorded by the principal investigator (or designee) on the AE eCRF. Study participants will be provided with a 24-hour telephone number to contact study personnel in case of an untoward reaction.

7.3 Reporting Requirements for Immediately Reportable Events

7.3.1 Principal Investigator's Reporting Requirements

The following events must be reported within 24 hours of awareness by the principal investigator (or designee) to sponsor's Global Pharmacovigilance Department (Global PV), through completion of the AE eCRF within the EDC system, and identifying the event as serious (SAE):

- Any SAE regardless of causal association with the IP.
- Any AESI regardless of causal association with the IP.
- Confirmed pregnancy of female participants.

Should the EDC system for reporting SAEs, AESI, and pregnancy be unavailable, the appropriate form(s) (listed below) will be completed and sent by email to the following address:

Global Pharmacovigilance Department

Emergent BioSolutions Inc.

The paper reported SAEs, AESI, and pregnancy should be entered in EDC once the system is available.

For SAE/AESI, the "Serious Adverse Event/Adverse Event of Special Interest Report Form" will be completed (abbreviated hereafter as "SAE/AESI Report Form"). The SAE/AESI Report Form is **not** the same as the AE eCRF. Supporting documentation that may be uploaded into the EDC to accompany the form(s) can include source documentation or medical records (eg, discharge summary for hospitalizations, lab reports) which support a diagnosis. Participant identifiers (eg, name, address, telephone number, social security number, medical record number, or hospital/laboratory number) must be redacted from the source documentation.

PXVX0317 Vaccine EBSI-CV-317-004, Version 5.0 20 Mar 2023

All SAEs that are unexpected (eg, adverse drug reactions) must be reported to the Institutional Review Board (IRB) by the investigator (or designee) as required by ICH GCP E6.

If a participant becomes pregnant during a study, the sponsor will be notified. All pregnancies where conception occurred after first exposure to the IP through the End of Study visit are to be followed to outcome (eg, delivery, spontaneous/elective/therapeutic abortion), including after the study is completed and even if the participant is withdrawn from the study. If a pregnancy results in an abnormal outcome that the reporting health care professional considers might be due to the IP, then the guidelines for expedited reporting of SUSAR should be followed (see Section 7.3.2).

Any pregnancy that occurs during study participation must be reported using the clinical study pregnancy forms ("Pregnancy Notification Form" and "Pregnancy Follow-up Form"). To ensure participant safety, each pregnancy must be reported to the sponsor within 24 hours of learning of its occurrence. The pregnancy must be followed up to determine outcome (including premature termination) and status of mother and child. Pregnancy complications and elective terminations for medical reasons must be reported as an AE or SAE. Spontaneous abortions must be reported as an SAE.

Any SAE occurring in association with a pregnancy brought to the investigator's attention during or after the participant has completed the study and considered by the investigator as possibly related to the study treatment, must be promptly reported to the sponsor.

The investigator is responsible to notify their IRB according to their policy.

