6.3 Derived Variables

This section provides definitions of the derived variables. In some cases, the definitions are provided in the relevant sections as noted.

AE, causing study discontinuation, is defined as a Yes response to the corresponding question on the AE eCRF.

AE, medically attended (MAAE), is defined as a Yes response to the corresponding question on the AE eCRF.

AE, **related**, is defined as one that is "probably" or "possibly" related to IP per investigator assessment on the eCRF. If the relationship is missing for one or more occurrences of an AE for a given participant, the closest relationship of the remaining occurrences of the AE for that participant is used; if the relationship is missing for the only occurrence of an AE for a given participant, then that event is assumed to be related in order to be conservative.

AE, resulting in death, is defined as a Yes response to the corresponding question on the AE eCRF and/or a fatal outcome.

AE, serious, is defined per the derived eCRF field for AE seriousness, based on the individual criteria that make an AE qualify as serious (results in death, is life-threatening, requires inpatient hospitalization or prolongation of existing hospitalization, results in persistent or significant disability/incapacity, or is a congenital anomaly or birth defect, or any event that may require medical or surgical intervention to prevent one of these outcomes).

AESI is defined in this study as new onset or worsening arthralgia that is medically attended, as noted by an AE having a Yes response to the corresponding AESI question on the AE eCRF.

AE, severity, is graded Grade 1 (mild) to Grade 4 (potentially life-threatening) as described in Section 5.9. If the severity is missing for one or more occurrences of an AE for a given participant, the maximum severity of the remaining occurrences of the AE for that participant is used; if the severity is missing for the only occurrence of an AE for a given participant, then that event is assumed to be severe in order to be conservative.

AEs, solicited, are defined as those collected in the electronic e-diary or paper diary. Solicited AEs include local (i.e., pain, redness, and swelling) and systemic reactions (i.e., fever, chills, fatigue, headache, myalgia, arthralgia, and nausea). *Solicited AEs were to be entered on Day 1 through Day 8; solicited AEs starting on Day 9 or later will be excluded from tabulations, with the exceptions of AESI and SAEs.*

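### Protocol 7.3.1, read literally, has sites mark every AESI and every confirmed pregnancy as serious, contrary to the protocol's own SAE definition

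*Protocol*

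**What the plan says.** Protocol 7.3.1 sets a 24-hour reporting duty to the sponsor's pharmacovigilance group, to be met "through completion of the AE eCRF within the EDC system, and identifying the event as serious (SAE"). That lead-in governs three list items: SAEs, "Any AESI regardless of causal association with the IP", and "Confirmed pregnancy of female participants". Nothing confines the serious label to the first item.

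Protocol 7.1.5 defines seriousness by outcome: "An SAE is any untoward medical occurrence that: results in death, is life threatening, requires inpatient hospitalization or prolongation of existing hospitalization", with disability and birth defect also listed. Other important medical events "may be considered an SAE when, based upon appropriate medical judgment, they may jeopardize the patient or participant". Neither AESI nor pregnancy appears as a criterion.

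Protocol 7.1.4 defines the AESI: "The occurrence of new onset or worsening arthralgia that is medically attended will be monitored throughout the study for all participants". Attendance may be at a hospital, an emergency room, an urgent care clinic or with any other medical personnel, apart from routine study visits.

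Later in 7.3.1, pregnancies go on dedicated notification and follow-up forms. Complications and terminations for medical reasons may be either AEs or SAEs, and spontaneous abortion is always an SAE.

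SAP 6.3 takes seriousness from a derived eCRF field built on the individual criteria, the last being "or any event that may require medical or surgical intervention to prevent one of these outcomes". It identifies an AESI by its own eCRF question.

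**The concern.** A reporting route and a seriousness classification are different things, and the lead-in of 7.3.1 merges them. A site that follows it to the letter classifies as serious some events that 7.1.5 does not. A site that follows 7.1.5 breaks the letter of 7.3.1. With up to 50 sites, both readings can be expected.

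Incidence of SAEs through Day 183 is a primary safety endpoint (Protocol 8.3.1). AESI incidence is listed alongside it and has its own tables. Seriousness is also one of the conditions for a SUSAR (Protocol 7.1.6 and 7.3.2) and for the investigator's report of unexpected SAEs to the IRB (7.3.1). Arthralgia is a solicited reaction and the only AESI, so its classification needs to be clean.

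**Working it through.** The plan states no expected rate of SAEs, AESI or pregnancies, so there is no figure to reproduce. The check is a comparison of the texts, followed by the little arithmetic that the documents allow.

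**1. AESI against the SAE definition.** Take a participant who visits an urgent care clinic for new knee pain and goes home.
- Under 7.1.4 this is an AESI.
- Under 7.1.5 no listed outcome is met, and the important-event clause needs a medical judgment about that case.
- Under the 7.3.1 lead-in it is identified as serious.

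The second and third results conflict.

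**2. Pregnancy against the SAE definition.** An uncomplicated pregnancy meets no 7.1.5 criterion. Later in 7.3.1, only spontaneous abortion is always serious, and complications may be non-serious. Those distinctions have no purpose if every confirmed pregnancy is already serious, so the section also conflicts with itself.

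**3. From the eCRF to the tables.** Under SAP 6.3 the event in step 1 has two possible paths:
- The site ticks no criterion. The derived field is not serious, the AESI question is answered yes, and the event appears in the AESI tables only. The analysis is right, but the letter of 7.3.1 is not followed.
- The site ticks a criterion in order to comply. The likeliest is the intervention criterion, which in the SAP lacks the reference to medical judgment found in 7.1.5. The event then becomes an SAE for analysis.

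The documents do not show how the data capture system builds the field, whether sites can set seriousness directly, or what triggers the notification.

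**4. Outputs touched on the second path** (SAP Appendix I):
- SAE and related-SAE tables 14.3.5.7 and 14.3.5.8, and SAE listing 14.3.4.1, gain the event.
- Table 14.3.3.5, which excludes SAEs, loses it.
- AESI table 14.3.5.9 is unchanged, because its flag is separate.
- Expedited reporting is affected only where the event is also judged related and unexpected.

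**5. Weight of one miscounted participant.** The denominators are 2700 vaccine recipients (Protocol 8.1.3) and 450 placebo participants (Protocol 3.1).
- Vaccine: 1/2700 = 0.037 percentage points.
- Placebo: 1/450 = 0.222 percentage points.

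**6. How far the size depends on assumption.** None of these rates is in the documents. Let b be the true SAE incidence and a the added incidence from misflagged events. The inflation is (b + a)/b.
- b = 0.5%, a = 0.1%: 0.6/0.5 = 1.2
- b = 0.5%, a = 1.0%: 1.5/0.5 = 3.0
- b = 1.0%, a = 0.1%: 1.1/1.0 = 1.1
- b = 1.0%, a = 1.0%: 2.0/1.0 = 2.0

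The result runs from 1.1-fold to 3.0-fold on assumptions alone, so it is not an estimate. If a and b are the same in both arms, both incidences rise and no difference between arms is created.

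**The case against.** The strongest reply is that the analysis ignores the reporting route. Under SAP 6.3 an AESI sent to pharmacovigilance with no criterion met is not an SAE in any table. The intervention criterion is limited to preventing the listed serious outcomes, and a clinic visit for joint pain does not meet it. No passage tells sites to tick an unmet criterion, and monitors verify entries against source (Protocol 9.3 and 10.1). The surrounding text also keeps the categories apart. Section 7.3 concerns immediately reportable events, the back-up form names SAE and AESI separately, 7.5.2 records them as distinct, and pregnancies have their own forms and outcome listing. The lead-in is probably a loosely worded notification trigger.

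Much of this stands. It makes any effect on the tables conditional, and pregnancies are the less likely route. It does not remove the contradiction: the sentence does not say that it is only a trigger, and a site cannot satisfy both 7.3.1 and 7.1.5 as written.

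Two stronger readings are tempting, and the documents support neither. A reader might infer that the SAE count would roughly double, but no SAE, AESI or pregnancy rate is given and step 6 shows that any multiple comes from the assumed inputs. A reader might also infer a bias against the vaccine. That needs more medically attended arthralgia on vaccine than on placebo. The documents give no such comparison, and Protocol 1.4 reports no concerning imbalance in unsolicited AEs to date.

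**Conclusion.** The contradiction is established from the text: the lead-in of Protocol 7.3.1 conflicts with 7.1.5, with 7.1.4 and with the pregnancy rules in the same section. It is an operating rule that misclassifies events if followed literally, so it should be corrected.

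Contamination of the SAE tables is possible but not shown. It requires a site to tick a criterion that the event does not meet, and the documents neither establish nor exclude this. The size cannot be estimated beyond the weight of each miscounted participant. Safety endpoints are descriptive (Protocol 8.6.2.5.2), so no hypothesis test or error rate is affected. What is at risk is the accuracy of a primary safety endpoint, the table of non-serious events and, in some cases, expedited reporting.

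**What to change.** Reconcile the passages in Protocol 7.3.1 and in the eCRF completion guideline:
- State that 7.3.1 sets only the 24-hour reporting duty for SAEs, AESI and pregnancies.
- State that an event is marked serious only when a 7.1.5 criterion is met, or under the existing 7.3.1 rule for spontaneous abortion.
- State that AESI and pregnancies are notified through the existing AESI question and pregnancy forms.

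New wording does not reach records already entered, and SAP 5.1.2 already describes site conduct in the past tense. So add a blinded check before database lock: list every AESI and pregnancy record flagged serious, with the criterion ticked, and query those where the source does not support it.

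The cost is a wording change, one listing and any resulting site queries. No endpoint, analysis method or sample size changes.

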7.3.2 Sponsor's Reporting Requirements

A SUSAR is a suspected adverse reaction that is both serious and unexpected (Section 7.1.6). As specified in 21 Code of Federal Regulations (CFR) 312.32, SUSARs will be reported by the sponsor of the Investigational New Drug Application (IND) to the FDA and to all participating principal investigators in an IND safety report as soon as possible, no later than 15 calendar days after the sponsor becomes aware of the suspected adverse reaction (21 CFR 312.32(c)(1)).

In addition, any unexpected fatal or life-threatening suspected adverse reaction will be reported to FDA no later than seven calendar days after the sponsor's initial receipt of the information (21 CFR 312.32(c)(2)).

7.4 Reporting of Other Information - Unanticipated Problems

As outlined by the Office for Human Research Protection, unanticipated problems must be reported to the IRB according to the requirements of 45 CFR Part 46. Unanticipated

problems are considered to include any incident, experience, or outcome that meets **ALL** the following criteria:

- Unexpected (in terms of nature, severity, or frequency) given:
 - Procedures that are described in the study-related documents, such as the IRB approved research protocol and informed consent document.
 - The characteristics of the participant population being entered into the study.
- Related or possibly related to participation in the study which means there is a reasonable possibility that the incident, experience, or outcome may have been caused by the sample collection.
- Suggests that the study places participants or others at a greater risk of harm (including physical, psychological, economic, or social harm) than was previously known or recognized.

An incidence, experience, or outcome that meets the three criteria above generally will warrant consideration of substantive changes in the study or informed consent process/document or other corrective actions in order to protect the safety, welfare, or rights of participants or others. Only a small subset of AEs occurring in human participants participating in a clinical study will meet these three criteria for an unanticipated problem. There are other types of incidents, experiences, and outcomes that occur during the conduct of a clinical study that represent unanticipated problems but are not considered AEs. For example, some unanticipated problems involve social or economic harm instead of the physical or psychological harm associated with AEs. In other cases, unanticipated problems place participants or others at increased risk of harm, but no harm occurs.

The investigator should promptly notify the IRB when an unanticipated problem involving risks to participants or others is identified. Also, the investigator should notify the sponsor of unanticipated problem(s).

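### Protocol 7.4 defines a study-related unanticipated problem by sample collection and does not name the investigational product; read literally, it leaves out non-serious problems caused by the vaccine

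*Protocol*

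**What the plan says.** Section 7.4 opens by requiring that unanticipated problems go to the IRB under 45 CFR Part 46. It then says that unanticipated "problems are considered to include any incident, experience, or outcome that meets" all of three criteria; the word all is emphasised in the text. In short, the event must be unexpected, must be related to the study, and must suggest more risk than was recognised before.

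The second criterion begins broadly, "Related or possibly related to participation in the study which means", and is completed at once by the definition: a "reasonable possibility that the incident, experience, or outcome may have been caused by the sample collection".

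The action attached to the definition is: "The investigator should promptly notify the IRB when an unanticipated problem involving risks to participants or others is identified". The section also states the consequence of meeting the definition: "An incidence, experience, or outcome that meets the three criteria above generally will warrant consideration of substantive changes in the study", or in the consent process, or other corrective action.

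Two further remarks in the section bear on its scope. It expects some adverse events to qualify: "Only a small subset of AEs occurring in human participants participating in a clinical study will meet these three criteria for an unanticipated problem". It also says that social or economic harm, or a raised risk without any harm, can count.

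**The concern.** The intervention in this trial is an injection of one of three vaccine lots or placebo (Protocol 3.1). Blood and urine sampling are supporting procedures. A relatedness criterion that names only sampling would suit a specimen-collection study; here it leaves out the product under test.

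What is at stake is whether the IRB is told of an unexpected, non-serious problem that comes from the vaccine, its administration or its handling. Section 7.4 is where the protocol links such problems to possible changes in the study or in consent. The point has some extra weight for participants aged 12 to <18, because the prior exposure cited in Protocol 1.4 is in 713 adults. With up to 50 sites, the scope of a reporting rule should not depend on each investigator choosing to read past its wording.

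**Working it through.** No arithmetic applies. The check sets the texts side by side.

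**1. How the criteria combine.** All three must be met, so an event that fails the second fails the definition. The notification sentence then does not apply to it.

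**2. What the second criterion says.** Its lead-in covers study participation in general. The words that follow the lead-in define it rather than illustrate it, and the definition names one cause, sampling. Take an unexpected, non-serious reaction to the injection that suggests a risk not previously recognised. By assumption it meets the first and third criteria. On the lead-in alone it meets the second. On the definition as written it does not, because the cause is the injection. The result turns on which half of one sentence the site applies.

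**3. Whether this agrees with the rest of the protocol.** It does not.
- Section 7.1.8 assesses causality of adverse events against the investigational product. An event graded there as probably related to the product does not, on that ground, satisfy the second criterion of 7.4.
- Section 7.4 itself expects some adverse events to qualify and mentions social and economic harm. That sits poorly with a cause limited to sampling.

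**4. Whether another rule fills the gap.**

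| Protocol section | Trigger | Recipient | Covers a non-serious, product-caused unanticipated problem? |
|---|---|---|---|
| 7.3.1 | Unexpected SAE | IRB | No: serious events only |
| 7.3.1 | AESI, serious or not | Sponsor's pharmacovigilance department, within 24 hours | The listed recipient is not the IRB |
| 7.3.1, closing sentence of the pregnancy text | Local IRB policy | IRB | Possibly; depends on that policy and on how far the sentence reaches |
| 7.3.2 | SUSAR | FDA and investigators | No: serious events only |
| 5.1.4, 5.1.5 | Shipment or storage excursion | Sponsor | No IRB step stated |
| 7.5, 7.5.1 | Non-serious AE | AE eCRF and follow-up | No IRB step stated |
| 7.6 | Two SMC reviews; ongoing medical monitor review | SMC and sponsor | No IRB step stated |
| 9.7 | Deviation needed to remove an immediate hazard | Sponsor and IRB | Only in that situation; no seriousness threshold |
| 12.2 | Protocol change to remove an apparent immediate hazard | IRB, within five working days | Only in that situation; no seriousness threshold |
| 11.2 | Amendment of protocol, consent form or Investigator's Brochure | IRB approval | Only once an amendment has been decided |

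Several routes touch the gap. None is an explicit trial-wide rule that sends a non-serious, product-related unanticipated problem to the IRB.

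**The case against.** The strongest reply is that Section 7.4, read as a whole, is plainly broad. It invokes 45 CFR Part 46, its definition is framed as one of inclusion, the lead-in speaks of participation in the study, and it foresees that adverse events, non-physical harm and even harmless events may qualify. A sensible investigator would see a slip of wording and would report a vaccine-caused problem anyway. Other safeguards also limit the harm. Immediate hazards reach the IRB under 9.7 and 12.2, and local IRB policy may prompt a report. Product excursions are quarantined and reported to the sponsor, wrong-treatment errors are protocol deviations (SAP 2.3.2), and the medical monitor and SMC review safety data.

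Most of this stands. It shows that the practical effect is probably limited and that the phrase was probably not intended as a restriction. It does not remove the defect. The broad reading requires the site to set aside the one clause that says what relatedness means. The sponsor, medical monitor and SMC routes do not go to the IRB, and the immediate-hazard rules cover a narrower situation.

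A reader might infer that a vaccine-caused, non-serious problem can never qualify, or that 7.4 is the only way such a risk could reach the IRB. The documents do not support either inference: the broader language in 7.4 and the partial routes in 7.3.1, 9.7 and 12.2 tell against both. Nor does 7.4 say that a qualifying event must lead to changes; it says that changes will generally need to be considered.

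**Conclusion.** The point holds in a limited form. As written, the second criterion conflicts with its own lead-in, with the section's expectation that some adverse events qualify, and with the product-based causality of 7.1.8. Its literal reading omits non-serious problems caused by the vaccine or its handling.

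The size cannot be estimated from the documents. It is tempting to take the planned 2700 vaccine recipients among 3150 participants as the number affected. Those are exposure figures, not missed reports. The first and third criteria already exclude most non-serious events, and the section itself expects few to qualify. Nor can all 3150 be assumed to be injected: enrolment means randomization (3.4.1), and 4.3.5 allows for withdrawal between randomization and treatment. The literal scope is also not a fixed number of blood draws, since urine is sampled (3.3.5, 3.3.7) and specimens may be repeated at unscheduled visits (5.2.10).

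The conclusion assumes that sites apply the definition as worded and that local IRB policy does not independently require the report. No endpoint, analysis, sample size, SAE route or SUSAR route is affected. It should be corrected because it is an operative safety-reporting rule and the correction is cheap.

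**What to change.** In the second criterion of Protocol 7.4, replace the closing words that attribute the cause to sample collection with: *caused by the procedures of the study, including administration of the investigational product and sample collection*. This brings the definition into line with its lead-in and with 7.1.8.

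The cost is one clause in a protocol amendment and possibly a few more reports to the IRB. The SAP needs no change.
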